**Table 11.4City of Hope Adverse Event and Unanticipated Problem Reporting Timelines for the DSMC and IRB**

**Required Reporting Timelines to DSMC for AE/SAEs**  
*Investigator Initiated Studies*

Required Reporting Timeframe to DSMC		
Attribution	UNEXPECTED	EXPECTED
	Death while on active treatment or within 30 days of last day of treatment	
Possibly, Probably, Definitely	5 calendar days	
Unlikely, Unrelated	Death after 30 days of last active treatment/therapy	
Possibly, Probably, Definitely	5 calendar days	No reporting required
Unlikely, Unrelated	No reporting required	No reporting required
	Grades 3 and 4 AND meeting the definition of "serious"	
Possibly, Probably, Definitely	5 calendar days	10 calendar days
Unlikely, Unrelated	5 calendar days	10 calendar days
	Grades 1 and 2 AND resulting in "hospitalization"	
Possibly, Probably, Definitely	5 calendar days	10 calendar days
Unlikely, Unrelated	10 calendar days	10 calendar days

An event determined by the IRB of record to be an Unanticipated Problem (UP) will be communicated to the Investigator and COH DSMC through the COH IRB Operations Director. The DSMC will review the case and make a determination as to whether the study will be suspended, terminated, amended, or allowed to continue without amendment.

Required Reporting Timeframe to IRB of Record		
Attribution	UNEXPECTED	EXPECTED
	Death	
Possibly, Probably, Definitely	5 calendar days	Annual
Unlikely, Unrelated	Annual	Annual
	Grades 3 and 4 AND meeting the definition of a UP	
Possibly, Probably, Definitely	5 calendar days	Annual

Required Reporting Timeframe to IRB of Record		
Attribution	UNEXPECTED	EXPECTED
Unlikely, Unrelated	Annual	Annual
	Grade 1 and 2 AND meeting the definition of a UP	
Possibly, Probably, Definitely	5 calendar days	Annual
Unlikely, Unrelated	Annual	Annual

### **Additional Reporting Requirements: FDA and National Institutes of Health - Office of Biotechnology Activities (NIH-OBA) Reporting**

Since this study involves gene therapy, and City of Hope holds the IND, adverse events must also be reported to the FDA and the NIH-OBA.

SAEs meeting the requirements for expedited reporting to the FDA, as defined in 21 CFR 312.32, will be reported as an IND safety report using the MedWatch Form FDA 3500A for Mandatory Reporting which can be found at: <http://www.fda.gov/Safety/MedWatch/HowToReport/DownloadForms/default.htm>

The PI or designee will be responsible for contacting the Office of IND Development and Regulatory Affairs (OIDRA) at COH to ensure prompt reporting of safety reports to the FDA and NIH-OBA. OIDRA will assist the PI with the preparation of the report and submit the report to the FDA and NIH-OBA in accordance with the following:

- Any unexpected fatal or life threatening adverse experience associated with use of the agent must be reported to the FDA no later than 7 calendar days after initial receipt of the information [21 CFR 312.32(c)(2)];
- Any adverse experience associated with use of the agent that is both serious and unexpected must be submitted no later than 15 calendar days after initial receipt of the information [21 CFR 312.32(c)(1)]
- Any follow-up information to a study report shall be reported as soon as the relevant information becomes available. [21 CFR 312.32(d)(3)]

The PI/designee will submit the adverse event report through the City of Hope electronic reporting system, and then OIDRA will take responsibility for reporting of the adverse event to NIH-OBA.

As required by the FDA, study patients will be followed long term (up to 15 years) and the PI will continue to report data and safety concerns to the FDA, DSMC, and IRB as they arise during this follow-up period.

### **Medical Device Reportable Events**

Medical devices that will be used in this study include intracerebral microdialysis catheters and Rickham reservoir/catheter systems.

Medical Device Reportable (MDR) Events are the AEs or problems that the medical device regulation requires to be reported. These events include patient deaths and serious injuries that the medical devices have or may have caused or contributed to, i.e., the devices may have directly caused the events or played a role in the events.

The timely reporting of MDR reportable events is required by the FDA, and will be handled by OIDRA.

## 12 CORRELATIVE/SPECIAL STUDIES

---

### **Intracerebral microdialysis**

---

In order to gather data regarding intracerebral levels of irinotecan and SN-38 when brain tumor patients are treated with CE-secreting NSCs and irinotecan, microdialysis catheters will be used to obtain samples of brain interstitial fluid, as described in sections 8.3, from the first 6 study patients and 8 patients treated at the MTD/MFD level in the expansion cohort. During dialysate collection, blood samples will also be drawn in order to compare systemic and intracerebral levels of irinotecan and SN-38 as described in sections 8.3.

Analysis will be performed by the City of Hope Analytical Pharmacology Core Facility.

### **Immunological Correlative Studies**

---

In order to 1) assess for possible development of T cell and antibody responses to the NSCs and/or cell surface-expressed adenoviral proteins, 2) measure adenoviral vector (Ad5) antibody titers and total adenoviral antibody titers, and 3) look for systemic presence of the NSCs and/or hCE1m6, samples of study patients' blood will be collected for isolation and storage of PBMCs and serum prior to surgery, on day 15 of cycle 1, days 1 and 15 of cycle 2, and on day 15 of subsequent treatment cycles. We will also test for replication competent retrovirus (RCR) (section 12.2.6).

The following studies, which were successfully performed in the first-in-human neural stem cell study of HB1.F3.CD NSCs and oral 5-FC, will be done by the City of Hope Clinical Immunobiology Correlative Studies Laboratory (CICSL), with the exception of the total adenoviral antibody titers, which will be performed by City of Hope Clinical Pathology:

#### **12.1.1 Assessment of the Development of Anti-NSC T Cell Responses**

---

Development of a T cell response to the adenovirally transduced NSCs will be evaluated by a combination of TCR V $\beta$  spectratyping and CD107 degranulation assays using established laboratory SOP and protocols. Briefly, V $\beta$  spectratyping of patient PBMCs collected prior to and after NSC administration will identify unique clonal populations of T cells that have expanded post-NSC administration. Such expanded populations have the potential to be specific for and to eliminate the administered NSCs. The specificity of the clonally-expanded T cells for the NSCs will be evaluated by 1) incubating pre- and post-infusion PBMC samples with the NSCs, followed by flow cytometric analysis using commercially available monoclonal antibodies specific for the identified clonotypes to determine the candidate T cells and 2) assessing surface CD 107 (a measure of cytotoxicity) on the surface of those T cells.

#### **12.1.2 Determination of Development of Antibody Responses to the Adenoviral Vector and/or NSCs.**

---

We will assess for development of antibody responses to the NSCs and/or cell surface-expressed adenoviral proteins.

An evaluation of humoral responses to NSCs will be performed in the CICSL by flow cytometric evaluation of antibody binding to NSCs. Briefly, aliquots of cultured NSCs will be incubated on ice with cryopreserved patient serum samples that have been heat treated to inactivate complement. Following incubation the NSCs will be washed and any bound antibodies will be detected using a secondary goat anti-human Fc antibody conjugated to FITC. After a second washing step, the NSCs will be analyzed by flow cytometry. Binding of human antibodies to the NSCs will be detected as a shift in the mean fluorescence intensity (MFI) compared to NSCs not treated with human serum. All samples obtained from individual subjects prior to and after therapy will be evaluated in parallel to evaluate possible development of humoral anti-NSC responses over time. The statistical significance of any detected MFI shifts will be evaluated by comparison with data from the NSC binding of a reference panel

of normal human sera. The assay will include as controls the parental NSC (not transduced with the CD gene) and the CD-expressing NSCs that have not been transduced with adenovirus to evaluate whether antibody responses are directed against the CD, CE, or adenoviral gene products.

If evidence of an immune responses are observed in patients, then we will assess for expression of the 72Kd DNA binding protein, which is specific to the adenoviral vector that was used to transduce the NSCs, and evaluate anti-hCE1m6 antibody titers to try to understand whether the immune response is to the NSCs themselves or the result of adenoviral transduction of the NSCs.

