
High-grade gliomas are difficult to treat due to their highly invasive nature and relative resistance to chemotherapy and radiation. Human neural stem cells (NSCs), modified to express a therapeutic transgene, hold great promise for glioma therapy due to their inherent tumor-tropic properties, enabling their use as vehicles for delivering chemotherapy directly to infiltrating glioma cells. This NSC-mediated delivery approach has the potential to overcome obstacles that limited gene therapy efficacy in the past and minimize off target toxicities of current treatment approaches.
 
Data from animal models have demonstrated the safety and efficacy of NSCs for tracking to invasive tumor cells as well as to distant micro-tumor foci and delivering therapeutic gene products to tumor cells. In our first-in-human pilot study of cytosine deaminase (CD)-expressing NSCs given in combination with oral 5-fluorocytosine (5-FC), we showed that 1 dose of CD-expressing NSCs followed by a 7 day course of 5-FC in recurrent high-grade glioma patients is safe and feasible. With intracerebral microdialysis, we documented proof-of-concept—that the NSCs converted the prodrug 5-FC to its active metabolite 5-FU locally in the brain. Results of immunologic correlative studies documented no findings of NSC immunogenicity after first exposure. Magnetic resonance imaging (MRI) of iron-labeled NSCs showed preliminary evidence of NSCs migrating away from the injection sites, and autopsy results from 2 study patients showed evidence that NSCs had traveled to distant sites of tumor in the brain.
 
This well characterized, v-myc-immortalized, clonal, human fetal NSC line has been further modified by adenoviral transduction to secrete a highly active modified human form (hCE1m6) of carboxylesterase (CE) for efficient conversion of irinotecan to its more potent metabolite, SN-38. We hypothesize that in patients with recurrent high-grade gliomas, CE-secreting NSCs will distribute throughout the primary tumor site as well as co-localize with infiltrating tumor cells within 2 days of administration. Study patients will then be treated with intravenously administered irinotecan. The CE-secreting NSCs will locally convert irinotecan to SN-38, thereby generating concentrated cytotoxicity at sites of tumor in the brain.

Objectives:

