We hypothesize that in patients with recurrent high-grade glioma, hCE1m6-NSCs will distribute throughout the primary tumor site as well as co-localize with infiltrating tumor cells within 2 days of administration. Study patients will then be treated with intravenously administered irinotecan. The CE-secreting NSCs will locally convert irinotecan to SN-38 (Figure 1), thereby generating concentrated cytotoxicity at sites of tumor in the brain.

**Figure1.** Schematic showing NSCs secreting CE enzyme, which converts irinotecan into the more cytotoxic SN-38.

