### 2.1.5 Preclinical Development of hCE1m6, A Modified Form of Human CE

Comparison of rabbit liver CE (rCE) to human CE (hCE1) revealed that the former enzyme more efficiently cleaved irinotecan to SN-38 (Danks, Morton et al. 1999; Bencharit, Morton et al. 2002). The reaction catalyzed by CE requires a relatively anhydrous environment, thus CEs have evolved to accommodate this by having a deep catalytic site, termed the catalytic gorge. Crystallographic studies revealed that for the human isozyme, large substrates such as irinotecan are unable to enter the catalytic gorge due to the lack of flexibility of the amino acids present in nearby loop domains (Bencharit, Morton et al. 2003). Based on these observations and extensive enzymologic studies carried out on CE, a chimera was designed incorporating sequences from the rabbit CE (rCE) enzyme into the human isozyme, hCE1 (Wierdl, Tsurkan et al. 2008). Eight amino acids were substituted in this engineered recombinant hCE which was termed hCE1m6 (Hatfield, Wierdl et al. 2008; Wierdl, Tsurkan et al. 2008). For preclinical development, our group chose to test both the rCE and hCE1m6 in parallel. The CE that performed the best in vitro and in preliminary in vivo microdialysis studies was to be carried forward in more extensive animal studies.

Our data supported the equivalence of hCE1m6 to rCE: (1) both enzymes had comparable enzymatic activity *in vitro*, (2) both equally sensitized glioma cells to irinotecan *in vitro*, (3) the conversion of irinotecan to SN-38 was roughly the same in rat brain when each were expressed by intracranially-administered NSCs and administered intracranially. Given the equivalency of the two enzymes in a variety of studies, the final choice to use hCE1m6 was based primarily on the potential for eliciting an immune response in humans using a lymphocyte degranulation assay. The hCE1m6-expressing NSCs caused less degranulation by CD4+ t cells than those expressing rCE. The difference in the degranulation response was statistically significant at  $p = 0.028$ .

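### The only direct test for antibody to the secreted enzyme hCE1m6 waits for an undefined trigger, so an isolated anti-enzyme response may go undetected

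*Combined protocol and SAP*

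**What the plan says.** The Introduction (section 2) describes the product's mechanism: "The CE-secreting NSCs will locally convert irinotecan to SN-38". The Protocol Synopsis likewise presents hCE1m6 as a secreted product of adenoviral transduction. On the enzyme itself, section 2.1.5 (as printed) states: "Eight amino acids were substituted in this engineered recombinant hCE which was termed hCE1m6". The inserted sequences come from rabbit carboxylesterase.

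The antibody subsection of 12.2 (printed as 12.1.2) defines the scheduled screen: "An evaluation of humoral responses to NSCs will be performed in the CICSL by flow cytometric evaluation of antibody binding to NSCs". In outline, "aliquots of cultured NSCs will be incubated on ice with cryopreserved patient serum samples"; the cells are washed, a labelled secondary antibody is added, the cells are washed again and fluorescence is read. Two control lines are included, parental NSCs and CD-expressing NSCs without adenovirus, with the aim "to evaluate whether antibody responses are directed against the CD, CE, or adenoviral gene products".

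The subsection then adds a second tier: "If evidence of an immune responses are observed in patients, then we will assess for expression of the 72Kd DNA binding protein". The same sentence, under the same condition, adds anti-hCE1m6 antibody titers.

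Section 12.1.3 (as printed) schedules Ad5 and total adenoviral IgG and IgM at baseline and at every immunology time point. Under 12.2, blood is drawn before surgery, on day 15 of cycle 1, on days 1 and 15 of cycle 2, and on day 15 of later cycles, and serum is stored. Immunogenicity after first and repeat exposure is a secondary objective. The Analysis Plan in section 15 summarizes it with descriptive statistics and graphs.

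**The concern.** A flow assay on washed cells reads antibody to whatever remains on the cell. No permeabilization step and no soluble-antigen step is described. An enzyme released from the cell may therefore be poorly represented, and antibody to it might cause little shift in fluorescence. The assay that would answer the question directly is reserved for patients who already show an immune response by some other route. It explains a response already seen; it does not screen for one.

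The enzyme, with the adenoviral step that introduces it, is what distinguishes this product from the CD-expressing cells of the first-in-human study. Section 2.1.5 says hCE1m6 was chosen over the rabbit enzyme mainly on immune potential, using lymphocyte degranulation; it reports no antibody data. Section 2.1.3 leaves open whether immune responses to repeat dosing of the CE-expressing cells will limit their use, and says this trial will investigate it. At stake is whether the repeat-dose immunogenicity objective can speak to the enzyme at all. Microdialysis would not fill the gap, because it is done only with the first irinotecan dose (Dose Escalation Schema, footnote b, in the Synopsis and section 5).

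**Working it through.** The documents give no sample size, power or detection rate for immunogenicity, so there is no plan figure to reproduce. The check is mainly textual.

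**Step 1. What each assay in 12.2 can show about anti-hCE1m6 antibody.**

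| Assay | Measured against | When run | Direct measure? |
|---|---|---|---|
| Flow antibody binding | Washed NSCs | Every scheduled sample | Only as far as enzyme stays on the cell |
| Ad5 and total adenoviral titers | Adenovirus | Every scheduled sample | No, different antigen |
| Spectratyping and CD107 | Transduced NSCs | Before and after NSCs, at the scheduled draws | No, T cells |
| Cytokine panel | None | Suspected immune response | No |
| Anti-hCE1m6 titer | hCE1m6 | After evidence of an immune response | Yes |

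The only row that measures the antibody directly has no scheduled time point, and no other section gives it one.

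**Step 2. What the flow control lines can separate.**

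| Line | CD | Adenovirus | CE |
|---|---|---|---|
| Parental | no | no | no |
| CD-expressing, untransduced | yes | no | no |
| Study product | yes | yes | yes |

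Three lines give 3 − 1 = 2 independent differences. CD line minus parental isolates CD. Product minus CD line gives adenovirus and CE together. There are three named targets, and no line carries adenovirus without CE, so these contrasts alone cannot separate the last two. They can also attribute only binding that the assay has already detected.

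**Step 3. Illustration of the consequence (assumed rates).** Let p be the true proportion of patients who develop anti-enzyme antibody. Let s be the chance that such a patient has the titer run, by any route. With independent patients and a perfect titer, P(no patient found) = (1 − p·s)^n. A routine titer corresponds to s = 1. The documents give neither p nor s. For n, section 15 states 14 patients at the MTD/MFD and an anticipated total of 29.

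| n | p | s = 0 | s = 0.25 | s = 0.5 | s = 1 |
|---|---|---|---|---|---|
| 14 | 0.10 | 100% | 70% | 49% | 23% |
| 14 | 0.20 | 100% | 49% | 23% | 4% |
| 14 | 0.30 | 100% | 34% | 10% | 0.7% |
| 29 | 0.20 | 100% | 23% | 5% | 0.2% |

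For example, at n = 14, p = 0.20 and s = 0.5: (1 − 0.10)^14 = 0.229. With a routine titer: 0.80^14 = 0.044, so at least one responder is found with probability 0.956. The gap closes only as s approaches 1.

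**The case against.** The best case for the plan has five parts.

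- **The trigger is broad.** It is not tied to the flow screen. A T cell signal, a rising adenoviral titer or clinical signs could each set it off. CD107 degranulation against the transduced cells is scheduled, and section 2.1.5 shows a degranulation assay distinguishing cells expressing the two enzymes (p = 0.028). This stands: a missed response is possible, not certain. But none of these signals is antibody to the enzyme, and the documents do not show that they accompany it.
- **The plan as a whole can separate CE from adenoviral responses.** A reader might infer from Step 2 that it never can. The documents do not support that, because the triggered anti-hCE1m6 titer and the scheduled Ad5 titers can do so. The limit applies to the flow controls alone.
- **Loss of signal from secretion is inferred.** A reader might conclude that the flow screen's sensitivity to anti-enzyme antibody is close to zero. The method is given only in outline, and nothing states how much enzyme remains on the cell. That conclusion is unsupported.
- **The stated endpoint is narrower than the enzyme.** The Synopsis names antibodies to the NSCs and to adenoviral proteins on the cell surface. This is true, but the antibody subsection names CE among the targets its controls will evaluate, so the plan does claim to cover it.
- **Little depends on the result.** No DLT, escalation or RP2D rule uses it, and section 6.1.5 bases stopping on clinical signs, not on antibody levels. Stored serum could be tested later. This limits the weight of the point but does not remove it: testing later still needs a decision that the plan does not contain.

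**Conclusion.** The concern holds as a gap in coverage. As written, an isolated antibody response to hCE1m6 may go undetected, and the flow control lines cannot deliver the CE-versus-adenoviral attribution claimed for them. The size cannot be fixed from the documents, since it depends on how much enzyme stays cell-associated and on how often another signal triggers the titer. The Step 3 percentages show the range under assumed values and estimate nothing about this trial.

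A reader might also infer that patients with only anti-enzyme antibody will be classed as non-immunogenic, so that the objective is biased toward a negative result. The documents do not go that far. Fluorescence shifts are compared with a panel of normal sera, but no rule classifies a patient as positive or negative overall, and the summary is descriptive. The supportable caution is narrower: the Introduction summarizes the earlier study's immunologic results as showing no NSC immunogenicity after first exposure, and similar wording here would claim more than the scheduled assays test. That anti-enzyme antibody would reduce irinotecan conversion on repeat dosing is plausible, but no section documents it.

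The point affects a descriptive secondary objective and leaves dose finding untouched. It is worth correcting because the remedy is specific and modest.

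**What to change.** In the antibody subsection of 12.2, make the anti-hCE1m6 titer a scheduled assay on every immunology serum sample: before surgery, cycle 1 day 15 (day 17 for dose levels 1 and -1, per the treatment schema), cycle 2 days 1 and 15, and day 15 of each later cycle. State that CE versus adenoviral responses will be attributed from the anti-hCE1m6 and Ad5 titers, and reword the purpose of the control lines to match what their contrasts can show. Add the anti-hCE1m6 titer to the immunogenicity endpoint in the Synopsis and section 15.

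If the titer stays conditional, define what counts as evidence of an immune response, and limit any negative immunogenicity statement to cell-bound and adenoviral antibody.

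The cost is laboratory work: four samples per patient through cycle 2, so at most 4 × 29 = 116 at the anticipated sample size if everyone gets that far, plus one per later cycle. No extra blood draws are needed. The protocol names the titer but describes no method for it, so some assay set-up may be required.

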#### **12.1.3 Measurement of Adenoviral Antibody Titers**

Serum adenoviral vector (Ad5) IgG and IgM antibody titers as well as total adenoviral IgG and IgM antibody titers will be assessed at baseline and then at the same time points when blood is collected for investigating the presence of T cell and antibody responses to the adenovirally transduced NSCs.

These blood samples will be sent to CICSL (adenoviral vector [Ad5] antibody titers) and Clinical Pathology (total adenoviral antibody titers) for processing and determining of adenoviral antibody titers by complement fixation testing and ELISA.

